Sample size was estimated based on the hypothesis that HBE would produce a difference of at least 10% in RDQ and SF-36 scores. Effect size (Cohen d) was calculated as 0,49 keeping in mind an RDQ mean and standard deviation of 3,3±1,0 previously found in Spanish population with symptomatic GERD²⁴ and an SF-36 mean and standard deviation of 56,9±20,3 reported in Italian population in medical therapy with PPI²⁵. The minimally important difference selection was chosen based on the assumption that any difference smaller than 10% would have no clinical relevance. Based on this data, 14 patients per group would yield a power greater than 80% for detection of a minimally important difference as large as or larger than 0,6 points in RDQ questionnaire (range: 1 to 6) and 10 points in SF-36 questionnaire (range: 0 to 100), when using a paired t test as described in the statistical analyses plan section. Because of a complementary analysis of crossover data is planned with McNemar marginal homogeneity test, effect size was recalculated based on results of a previous trial²⁰, according to which, 58,8 % and 28,6% of placebo-treated patients in pre-omeprazole era, reported improvement of GERD symptoms with and without a HBE of 20 cm, respectively. Based on these data, and maintaining a statistical power of 80%, required sample size was adjusted to a total of 34 patients. In

figure 2, matrices for sample size calculation are shown, based on the cited trial and using internationally accepted statistical procedures²⁶. Likewise, in table 3 an output of sample size calculation is shown from G*Power 3.1.9.2 (Universität Düsseldorf, Düseldorf, Germany) software²⁷. Finally, calculated sample size was increased by 20% in order to avoid study power loss due to drop-outs or losses of follow-up. Thus, final sample size was 42 patients, 21 per group.

T test	Means: Difference between two dependent means	(matched pairs)
Analysis	A priori: Compute required sample size	
Input	Tails	One
	Effect size dz	0,4926108
	A err prob	0,05
	Power (1- β err prob)	0,8
Output	Noncentrality parameter δ	2,5596808
	Critical t	1,7056179
	Degrees of freedom	26
	Total sample size	27
	Actual power	0,8015888
McNemar	Proportions: Inequality, two dependent groups	
Analysis	A priori: Compute required sample size	
Input	Tails	One
	Odds ratio	3,571
	α	0,05
	1- β	0,8
	Prop discordant pairs	0,53782
Output	Lower critical N	13,0000000
	Upper critical N	13,0000000
	Total sample size	34
	Actual power	0,8169370

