Design and carving of wooden prisms: 124 prisms of withered pine tree wood with dimensions 20x18x18 cm will be carved from 9 logs of 300x20x20 cm at Aserrío San Ignacio Ltda. production plant, located in Soacha, Cundinamarca. Given it is an industrial process of chainsaw cutting and wood planning, a quality control will be implemented consisting of verification of prism stability while lying on the floor, and the mean height in millimeters of every prism will also be measured and registered. Unsteady products or those with atypical mean heights, defined as a height either exceeding percentile 75 + 1,5 times interquartile range or below percentile 25 - 1,5 times interquartile range, will be discarded and not used during the study. As shown in figure 3, this non-pharmacological intervention was designed to obtain an inclination range dependent on the bed length of each patient (usually 1,90 cm in local industry). After exclusion of defective prisms, n groups of wooden prism pairs according to mean height in millimeters will be formed and every group will be given a random digit generated by computer. Afterwards, every random digit of prism groups will be sequentially assigned to a consecutive HBE-allocated patient number, in such a way that every consecutive patient number (among those allocated to HBE) will be linked randomly to a preset known prism height. This additional randomization procedure, involving prisms according to their mean height, is planned due to the impossibility to guarantee that prism height will be identical with a precision of ±1 mm, keeping in mind that products will be cut with chainsaw and will be planed as part of an industrial process.

	Improved with treatment B					
Improved with treatment A	No	Yes	Total			
No	r	S	r+s			
Yes	t	u	t+u			
Total	r+t	s+t	N pairs			

Discordant pairs =
$$\frac{s+t}{N \ pairs}$$
 = 53,8% $OR = \frac{s}{t} = 3,57$

	Improved without HBE					
Improved with HBE	No	Yes	Total			
No	29,4%	11,8%	41,2%			
Yes	42%	16,8%	58,8%			
Total	71,4%	28,6%	100%			

Figure 2: Matrices for sample size calculation, according to reference 20 and 26. HBE: Head of Bed Elevation.

In figure 4, a quality control graph is shown. Mean wooden prism height was a non-normal variable when Shapiro-Wilk test was applied (W: 0,908; critical W: 0,979; p: 0.000000). After using predefined exclusion rules for atypical values, 2 pairs of wooden prisms were discarded.

[figure not shown]

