Statistic analysis plan: Quantitative and qualitative variables collected with Basic Data Format, RDQ, SF-36 and Patient Preference questionnaires will be typed in a Microsoft Excel 2007 database. Intervention groups will be masked with an alphabetical code provided by an independent collaborator who will not be involved with data analysis or report writing. For statistical processing, database will be imported into STATA SE 13.0 for Windows (StataCorp LP, Texas, USA) and descriptive statistics will be generated for each variable. Statistically significant differences will be searched for categorical data using the Chi-square test or Fisher exact test and normality will be tested for numerical continuous variables using the Shapiro-Wilk test. For normally distributed continuous variables, statistically significant differences will be searched for by using unpaired Student's t test. Alternatively, for not normally distributed variables Mann-Whitney U test will be applied. For non-normal variables due to atypical data, values outside the percentile 50 ± 1,5 interquartile range were excluded. For complementary processing of primary outcome and secondary outcome quality of life, score difference

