between periods will be transformed into a binomial variable and a McNemar marginal homogeneity test will be applied. McNemar mid-p was used if discordant pairs sum was smaller than 25²⁸. Differences with one-tail p<0,05 will be accepted as statistically significant. Exploratory subgroup analysis will search for differences stratified according to age group, sex, ethnic group, BMI, comorbidities, cups of coffee per day, pharmacological adherence, and length and severity of symptoms; among other 16 baseline variables. Subgroup interactions will be tested with Chi-square or Fisher exact test, and effect size was expressed as a univariate relative risk from a generalized linear model of binomial family. As part of internal quality control of the clinical trial, a pre-test was applied to prove the assumption of a negligible *carry-over* effect, according to expert guidelines²⁹. Analysis of variance (ANOVA) for crossover studies was used in search for significant sequence, period and treatment effects, assuming a negligible *carry-over* effect. In the modified intention to treat analysis, participants with protocol violations because of bad adherence to HBE, were included, but it was not possible to include patients who withdrew from the study because outcome information could not be gathered completely.

Methodology diagram: A schematic representation of the trial methodology is presented in figure 6.

[figure not shown]

Figure 6: Schematic representation of the trial methodology. RDQ: Reflux Disease Questionnaire; SF-36: Short Form 36 Questionnaire; HBE: Head of Bed Elevation; Standard treatment: Based on proton pump inhibitors and/or sodium alginate, according to treating physician criteria.

WORK TEAM

Work team of this clinical trial is formed by three authors. The respective roles during the design and conduction of the trial, and also the professional profiles of each researcher are described below.

Researchers:

- [name] (Principal Researcher study design, patient recruiting, telephonic follow-up, outcome assessment, statistical analysis, writing of final report)
 - General Practice Physician Universidad Nacional de Colombia
 - 3rd year Internal Medicine resident Universidad Nacional de Colombia
- [name](Researcher patient recruiting, intervention administration, clinical and telephonic follow-up, writing of final report)
 - General Practice Physician Universidad Nacional de Colombia

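### The rule excluding values beyond median ± 1.5 IQR can delete genuine RDQ and SF-36 outcomes and bias the HBE comparison

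*Combined protocol and SAP*

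**What the plan says.** The Statistic analysis plan opens by listing the data it covers: "Quantitative and qualitative variables collected with Basic Data Format, RDQ, SF-36 and Patient Preference questionnaires will be typed in a Microsoft Excel 2007 database". It then states that "normality will be tested for numerical continuous variables using the Shapiro-Wilk test", without giving a significance level for that test. Normally distributed variables go to an unpaired t test; "for not normally distributed variables Mann-Whitney U test will be applied". The next sentence is the rule at issue: "For non-normal variables due to atypical data, values outside the percentile 50 ± 1,5 interquartile range were excluded".

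The Sample size paragraph gives the two scales and the differences of interest: "0,6 points in RDQ questionnaire (range: 1 to 6) and 10 points in SF-36 questionnaire (range: 0 to 100". Its planning value for the primary score is "an RDQ mean and standard deviation of 3,3±1,0 previously found in Spanish population"; for SF-36 it uses 56.9 ± 20.3.

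On the analysis set, the plan says that "it was not possible to include patients who withdrew from the study because outcome information could not be gathered completely". It mentions no other loss of data there.

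The protocol uses a different outlier rule for hardware. Under Design and carving of wooden prisms, a prism is discarded for a height "exceeding percentile 75 + 1,5 times interquartile range or below percentile 25 - 1,5 times interquartile range".

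**The concern.** Removing an outcome after randomisation because of its value is a different matter from correcting an error. RDQ and SF-36 are bounded scales, so a value inside the range can be a genuine answer. If the patients who did much better or much worse are cut, the estimated effect of HBE moves, and the variance is understated as well.

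The sentence leaves these points open:

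- what shows that atypical values are the cause of the non-normality;
- whether the limits are formed per treatment, on pooled data or on within-patient differences;
- whether deletion comes before or after the choice of the rank test;
- what happens to the other half of a crossover pair when one value is removed.

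These choices give different results, so the analyst has a decision to make that can change the primary comparison. The deletion is also unnecessary, because the preceding sentence already provides a rank test for non-normal variables. The main verb is in the past tense, so the rule may already have been applied.

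**Working it through.** **Inputs.** From the plan: limits at median ± 1.5 IQR; RDQ 3.3 ± 1.0 on 1 to 6; SF-36 56.9 ± 20.3 on 0 to 100; one-sided 0.05; 34 evaluable patients from the McNemar calculation. That calculation reproduces: 34 × 0.53782 = 18.3 discordant pairs, taken as 18; with critical value 13, alpha is 0.0481 and power 0.8169, as in Table 3. The plan gives no figure for the number of values the rule removes.

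**Width of the limits.** For a normal shape, IQR = 1.349 SD.

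- Outcome rule: 1.5 × 1.349 = 2.02 SD either side of the median. Share outside: 2 × (1 − Φ(2.02)) = 4.3%.
- Prism rule: 0.674 + 2.023 = 2.698 SD. Share outside: 2 × (1 − Φ(2.698)) = 0.7%.

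The rule for outcomes is therefore tighter than the rule for wooden blocks.

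**Position on the scales**, taking the median as the planning mean:

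- RDQ: 3.3 ± 2.02 × 1.0 = 1.28 to 5.32. Valid scores of 1.00–1.27 and 5.33–6.00 fall outside.
- SF-36: 56.9 ± 2.02 × 20.3 = 15.8 to 98.0.
- RDQ if the IQR is 1.0: 3.3 ± 1.5 = 1.80 to 4.80. If it is 1.5: 3.3 ± 2.25 = 1.05 to 5.55.
- The RDQ minimum of 1 survives only if 1.5 × IQR ≥ 3.3 − 1 = 2.3, that is IQR ≥ 1.53.
- Prism-type limits on RDQ: 3.3 ± 2.698 = 0.60 to 6.00, which removes essentially nothing.

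**Effect on the tests (assumed data shapes).** Each scenario has 6,000 simulated trials of 34 pairs, with deletion when Shapiro-Wilk p < 0.05. The simulation standard error of a 5% rate is √(0.05 × 0.95 / 6,000) = 0.3 percentage points.

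(a) Skewed scores, no effect: score = min(6, 1 + exp(0.6 Z)), correlation 0.5 between periods. Paired tests use complete pairs; unpaired tests compare all remaining HBE and control scores. One-sided type I error:

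| Test | All data | Limits per treatment | Pooled limits | Limits on differences |
|---|---|---|---|---|
| Paired t | 5.2% | 10.4% | 5.3% | 8.1% |
| Signed-rank | 5.1% | 9.2% | 5.3% | 7.4% |
| Unpaired t | 1.2% | 8.9% | 2.4% | – |
| Mann-Whitney | 1.1% | 5.8% | 2.1% | – |

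The unpaired tests start near 1% because they ignore the correlation within patients.

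(b) Limits on differences; 85% better by 0.3 points and 15% worse by 1.7, SD 0.5. True mean: 0.85 × 0.3 − 0.15 × 1.7 = 0. With the rule, the average estimate is 0.21 in favour of HBE. HBE is declared better, with v without the rule, in 70% v 7% (t test), 71% v 22% (signed-rank) and 57% v 12% (McNemar mid-p, counting differences of at least 0.6 points).

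(c) Limits on differences; 15% better by 2.0, the rest unchanged, SD 0.5. True mean: 0.15 × 2.0 = 0.30. With the rule, the average estimate falls to 0.10. Power, with v without the rule, is 26% v 65% (t test), 20% v 40% (signed-rank) and 18% v 44% (McNemar mid-p).

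About 4 of 34 differences are deleted in (b) and (c).

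**Direction.** Further runs (20,000 trials, limits on differences, paired t test, SD 1, zero mean effect):

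- A skewed tail of worsening moves the estimate 0.24 towards HBE, and rejection goes from 9.4% to 64.4%.
- The mirror image moves it 0.24 against HBE, and rejection goes from 2.3% to 0.4%.
- Symmetric heavy tails (t, 4 df) leave the estimate unbiased, but type I error goes from 5.2% to 8.0%.
- Normal data go from 5.0% to 5.7%.

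**The case against.** No sentence says outright that outcome values are deleted. The rule closes a general block that also covers baseline data, where outlier screening would not touch the treatment effect. This limits how firmly the scope can be read, but RDQ and SF-36 are named at the start of that block, neither is exempted, and the next sentence describes McNemar as a complement for these same outcomes.

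The limits of 1.28 to 5.32 assume a normal shape and a median of 3.3, whereas the rule applies only to non-normal data and trial patients are on acid-suppressing or alginate treatment. This stands: those figures show the width of the limits, not expected deletions. In scenario (a) the median is 2.00 and the IQR 0.83, so the limits are 0.75 to 3.25, the scale minimum survives, and nearly all cuts are high scores.

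The large numbers come from chosen mixtures and from limits on differences, which the plan does not specify. Signed-rank is not in the plan, and carrying deletions into the McNemar variable is an assumed reading. In (b), zero mean effect is not a null for signed-rank or McNemar, so their increases are not purely false positives. All of this stands. So does the point that pooled limits cause no inflation for the paired tests in (a), and that Mann-Whitney reaches only 5.8%, although that is about five times its all-data rate.

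The analyst works with coded groups, which makes deliberate misuse less likely. Coding does not stop value-dependent deletion from biasing skewed data, and the Work Team section gives the principal researcher follow-up, outcome assessment and statistical analysis.

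Finally, the exclusion is stated openly in the plan, so its absence from the analysis-set sentence is a minor matter.

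**Conclusion.** The concern holds, and the rule must be fixed. As written it permits deletion of genuine RDQ and SF-36 responses on an undefined judgement, with limits that can lie inside both scales, and this can bias the HBE comparison in either direction. The finding that the rule is unsuitable rests on the text and on the simple arithmetic for the limits.

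The size in this trial cannot be known from the documents. It runs from no inflation (paired tests, pooled limits) through a doubling of type I error (paired t, limits per treatment) to a reversed conclusion when about 4 of 34 differences are cut from a mixed population. These sizes depend on the assumed shapes, on Shapiro-Wilk p < 0.05 as the trigger and on where the limits are formed. Bias in the estimate needs skewed or mixed data; with symmetric data the main harm is an understated variance. The sample-size figures are unaffected.

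**What to change.** Delete the exclusion sentence for patient outcomes and replace it with text such as:

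> Every recorded RDQ and SF-36 value will be analysed. Only verified data-entry errors will be corrected, before unmasking. If within-patient differences are not normal, a rank-based test on those differences that suits the crossover will be used.

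One suitable test is a rank-sum comparison of within-patient period differences between the two sequences.

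A trimmed result may be reported only as a labelled sensitivity analysis. It should state the trigger, whether the limits are per treatment, pooled or on differences, and how many values were removed under each treatment.

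The cost is one sentence and no extra data. If values have already been excluded, they should be restored and the analysis rerun.

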Methods: Randomized single-blind single-centre controlled clinical trial with a 2x2 cross-over design. A sample of 42 patients attending to the outpatient gastroenterology unit at Clínica Fundadores in Bogotá city, who meet the inclusion criteria and have no exclusion criteria will be selected to participate. Included patients will be randomized to raise the head of bed with standard 20 cm-height wooden blocks or to sleep without bed inclination during the first 6 week period. After a 2 week washout period, allocation will be crossed and participants will be followed again during a second 6 week period. During the trial, every patient will receive standard pharmacological treatment with a proton pump inhibitor and/or sodium alginate and the researchers in charge of statistical analysis and reporting results will be blinded for the non pharmacological intervention under study. Primary outcome is a significant symptom reduction according to RDQ validated questionnaire and secondary outcomes include quality of life impact according to SF-36 validated questionnaire, patient preference and adverse events of non pharmacological intervention. Statistical analysis will be carried out with STATA 13.0 (Special Edition) statistical package for Windows. Differences with a p<0,05 will be accepted as statistically significant.

Expected results: Effectiveness of head of bed elevation in the treatment of patients with symptomatic nocturnal gastroesophageal reflux disease will be assessed. New knowledge for generation of a local and international recommendation about non pharmacological treatment of gastroesophageal reflux disease will be provided. Colombian researchers will be trained in methodological aspects concerning design, conduction and analysis of clinical trials in this field of medical knowledge.

Keywords: Gastroesophageal reflux disease, head of bed elevation, lifestyle measures, nocturnal symptoms, quality of life.

PROBLEM STATEMENT

Gastroesophageal reflux disease (GERD) is a clinical condition characterized by troublesome symptoms and medical complications as a result of reflux of gastric contents into the esophagus¹. GERD is diagnosed in 4% of primary care outpatient visits² and the disease prevalence in Latin-America reaches 12-31%³. Nocturnal symptoms have been found in 74% of patients with GERD and are a cause of significant quality of life impairment, when compared with general population and

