The trial will be conducted during 8 months and will be divided into 4 successive stages.

- 1. Stage I: 2 months during which the first 4 specific objectives will be accomplished.
- 2. Stage II: 4 months for specific objectives 5 to 7.
- 3. Stage III: 1 month for specific objective 8 and results discussion.
- 4. Stage IV: 1 month for specific objectives 9 and 10.

In figure 1 and table 2, different stages with respective component activities are outlined.

[figure not shown]

Figure 1: Clinical trial stages

Patient recruitment: Because of a low recruitment rate, an active participant search system was finally implemented. This system was based on telephone calls, using a database with patient data from all upper gastrointestinal endoscopies performed in the Gastroenterology Unit at Clínica Fundadores in Bogotá city, between years 2014 to 2016. Patients were pre-selected based on endoscopically diagnosed erosive esophagitis of any grade, which is one of the clinical trial inclusion criteria. In order to minimize selection bias, 2 interviewers performed telephone calls in a consecutive chronologic order to all patients in the database without exception. In all cases, the same standardized telephone call format was used.

Sample size: Null hypothesis (H_0) and unidirectional alternative hypothesis (H_1) of the trial are represented below:

$$H_0$$
: RDQ_{HBE}= RDQ_{NoHBE} H_1 : RDQ_{HBE}< RDQ_{NoHBE} H_0 : SF-36_{HBE}= SF-36_{NoHBE} H_1 : SF-36_{HBE}> SF-36_{NoHBE}

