Follow-up: After participant allocation, telephonic follow up will be made during both periods of the trial with a frequency that is dependent on the intervention group of the patient in that period. Participants in the HBE group will be called weekly for 2 weeks, and then will be called biweekly for a month, until each period of 6 weeks has ended. In contrast, patients in the control group will be called every three weeks along each period. With the purpose of verifying both HBE adherence and correct use of wooden prisms, every participant will be asked to send a photograph of the bed head legs during the follow-up telephone call. The photograph will be received by the researcher via e-mail or smartphone and will be encoded and saved in a hard disk. At the end of the first period, RDQ and SF-36 questionnaires will be applied and researchers will store the returned prisms during washout period. When washout period has ended, RDQ and SF-36 questionnaires will be applied again in order to be sure of the absence of any carry-over effect in the group initially allocated to HBE. Finally at week 14, RDQ, SF-36 and Patient Preference questionnaires will be administered to complete study ending outcome assessments.

In figure 5, a schematic representation of follow-up is shown.

[figure not shown]

Figure 5: Schematic representation of photographic and telephonic follow-up. W1-6: Weeks from 1st to 6th in each period.

Primary outcome:

1. Effectiveness: Change of ≥ 0,6 points between basal RDQ questionnaire and the same questionnaire administered after 6 weeks of HBE use.

Secondary outcomes:

- 1. Quality of life: Change of ≥ 10 percentage points between basal SF-36 questionnaire and the same questionnaire administered after 6 weeks of HBE use.
- **2. Patient preference:** Proportion of patients who preferred HBE, after finishing 14 weeks of the study.
- 3. Safety: Proportion of patients with any reported adverse event during HBE or without bed inclination.

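### The analysis plan's only significance rule is an unrestricted one-tail p<0.05, but a direction is declared only for RDQ and SF-36, so the rule is undefined or misfires for adverse events and the other undirected comparisons

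*Combined protocol and SAP*

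**What the plan says.** **Significance rule.** The Statistic analysis plan states "Differences with one-tail p<0,05 will be accepted as statistically significant". The sentence comes after the chi-square, Fisher, unpaired t, Mann-Whitney and McNemar tests. It comes before the subgroup tests, the carry-over pre-test and the crossover ANOVA for sequence, period and treatment. No other significance level is given for any of these.

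**Declared direction.** The Sample size section says that the null and "unidirectional alternative hypothesis (H_1) of the trial are represented below", and then lists two: RDQ lower with HBE and SF-36 higher with HBE. Table 3 uses one tail for both of its calculations.

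**Outcomes without a direction.** Safety is defined as "Proportion of patients with any reported adverse event during HBE or without bed inclination". Patient preference is the proportion who preferred HBE. Neither has a stated direction or a test of its own.

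**Executive summary.** The Methods paragraph says "Differences with a p<0,05 will be accepted as statistically significant", with no mention of tails.

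**The concern.** A one-tail test is defined only when its tail is fixed in advance. For RDQ and SF-36 it is. For adverse events, patient preference, baseline characteristics, sequence, period, carry-over and subgroups it is not, yet the only rule on the page is one-tailed. An analyst who follows the text has two choices. Taking the tail that the data point to gives a larger error rate than the stated 5%. Carrying over the efficacy direction leaves a test that cannot register harm from HBE.

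Safety is a listed secondary outcome of a trial meant to inform recommendations, so neither choice is acceptable there. A reader who sees only the summary will probably take p<0.05 as two-sided.

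**Working it through.** **1. The plan's own figures are one-tailed and reproduce.**
- Paired t, with dz = 0.4926108, one tail, alpha 0.05 and n = 27. Noncentrality = 0.4926108 × √27 = 2.5597, critical t on 26 df = 1.7056, power = 0.8016. All match Table 3.
- McNemar, with odds ratio 3.571, discordant proportion 0.53782 and n = 34. Expected discordant pairs = 34 × 0.53782 = 18.3, taken as 18. Rejecting at 13 or more gives alpha 0.0481 and power 0.8169. Both match Table 3.
- Drop-out: 34 × 1.2 = 40.8 and 34 / 0.8 = 42.5. The final 42 is consistent with either.

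One-tail testing of RDQ and SF-36 therefore agrees with the hypotheses and the sample size.

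**2. Size when the tail follows the data.** For a symmetric statistic, size = P(smaller one-tail p < 0.05) = 2 × 0.05 = 0.10.
- *Unpaired t:* in 100,000 simulated null trials with 21 per group, the smaller one-tail p was below 0.05 in 10.2%. Mann-Whitney follows the same argument.
- *McNemar:* doubling Table 3's actual alpha gives 2 × 0.0481262 = 0.0963. The plan names McNemar for RDQ and quality of life, which have a direction, so this matters only if it is also used for an undirected paired outcome such as adverse events.
- *ANOVA F:* the test has one rejection region, the upper tail, which covers both directions. In the same simulation it rejected in 5.1%. There is no inflation unless the p-value is halved. Ordinary chi-square behaves in the same way.
- *Fisher:* the size depends on the event rate, which the documents do not give. I assumed 17 per group and a common event rate π, and summed Bin(i; 17, π) × Bin(j; 17, π) over all tables with p < 0.05:

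| π | Two-sided | Tail chosen from data |
|---|---|---|
| 10% | 0.8% | 1.0% |
| 20% | 1.9% | 3.7% |
| 30% | 2.0% | 4.5% |
| 50% | 2.4% | 5.8% |

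Across group sizes near this trial's, the ranges are about 1-3% two-sided and 1-7% with a data-chosen tail. Fisher is so conservative here that the rough doubling leaves it near 5%.

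**3. Size when the tail is fixed as HBE better.** Suppose adverse events are more frequent on HBE with a two-sided p of 0.01 (symmetric statistic). The one-tail p in the benefit direction is 1 − 0.01/2 = 0.995. Stronger evidence of harm moves p closer to 1, so the rule can never flag it.

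**The case against.** **The rule may not be meant for every test.** It directly follows the McNemar analysis of the two outcomes that have a direction, and the subgroup, carry-over and ANOVA sentences come later. That narrower reading is possible. It leaves all other tests with no stated threshold or tail, so the same clarification is needed.

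**A reader might infer 10% error for every undirected test.** The documents do not support this. Sequence and period are tested by ANOVA, and categorical data and subgroup interactions by chi-square or Fisher. None of these reaches 10% unless a chi-square or F p-value is halved, which the plan does not propose.

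**A reader might also compute an inflated subgroup error.** With 24 variables, 1 − 0.95^24 = 71% becomes 1 − 0.90^24 = 92%. This fails because the interaction tests do not run at 10%. It also assumes independent tests and one count from wording that allows 16 to 25. The 71% at a proper 5% level is a multiplicity matter in an analysis labelled exploratory.

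**Harm to the safety comparison is conditional.** No adverse-event test is named; one is only implied by the general sentence on categorical data. Nothing says the tail would be HBE better, and the proportions in both conditions are a stated outcome whatever the p-value. This stands: the blocked test follows from one of two open readings and is not a stated plan.

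**Carry-over runs the other way.** The pre-test checks an assumption on which the ANOVA rests, so the costly error is missing carry-over. A stricter level would make that more likely. This also stands and shapes the fix.

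**Conclusion.** The point holds as a stated rule that misfires outside the two comparisons with a declared direction. Where the tail follows the data, the size is about 10% for t, Mann-Whitney and McNemar tests and for any halved chi-square or F p-value. For Fisher it stays near 5%, on assumed event rates of 10% to 50%. Ordinary chi-square and F tests are unaffected. Where the tail is taken as HBE better, harm cannot be flagged.

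Two further inferences should be resisted. The summary does not contradict the plan, because it omits the tail and does not claim two-sided tests. One-tail testing of RDQ and SF-36 is not an error, because it matches the declared hypotheses and Table 3. The primary comparison and the sample size are untouched. The clarification is worth making because safety is a listed outcome and the change costs only wording.

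**What to change.** - Limit one-tail 5% to the RDQ and SF-36 hypotheses in the Sample size section.
- State two-sided 5% for all other comparisons: adverse events, patient preference if tested, baseline, sequence, period and subgroup tests. Say that chi-square and F p-values for these are not halved.
- For the carry-over pre-test, state a two-sided test with its own level, and do not tighten it. One-tail 5% with a data-chosen tail already amounts to two-sided 10%, so a lower two-sided level would be stricter than the present rule allows.
- Report two-sided 95% confidence intervals for all HBE-control differences, including adverse events.
- State the tail in the executive summary, in the same words.

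**Cost.** No extra patients: the requirement stays at 34 and the final number at 42. Some secondary and exploratory p-values double. For RDQ and SF-36, a one-tail p between 0.025 and 0.05 will go with a 95% interval that includes no difference, and the report should say so openly.
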